### **C.4 Study population**

Approximately 20 subjects with Chronic Heart Failure will be enrolled in the study. No control group will be used for this study.

### **C.5 Study design**

This is a prospective, non-randomized, single-center post-market interventional study. The Study will take place in the Netherlands at one investigation site.

### **C.6 Randomization and blinding**

No randomization and no blinding will be used in this Study.

### **C.7 Sample size**

The FRAP study is primarily designed to evaluate the possibility of extracting walking patterns from the accelerometer embedded in the Reveal LINQ.

A sample size of approximately 20 subjects will be enrolled to see if reproducible results indicating feasibility of extracting walking patterns could be obtained. No formal statistical hypotheses are being tested.

### **C.8 Number of investigation sites and study duration**

The single participating center is the NUTRIM School of Nutrition and Translational Research in Metabolism of the Faculty Health, Medicine and Life Sciences, Maastricht University, Maastricht, The Netherlands. Approximately 20 subjects will be enrolled in the study and it is expected that the subjects will be enrolled over a period of 3 months and no follow up beyond the single visit is envisaged.

## **D SUBJECT SELECTION**

### **D.1 Inclusion criteria**

- Chronic Heart Failure in NHYA class II and class III.
- Willing to sign the informed consent form.
- At least 18 years of age.

### **D.2 Exclusion criteria**

- Not able to walk continuously for a period of 6 minutes and perform the walking exercises as necessary for the study protocol.
- Any known allergy to Titanium
- Any concomitant conditions which in the opinion of the investigator would not allow accurate measurement of gait and frailty parameters with an externally worn device.
- Any concomitant condition which in the opinion of the investigator would not allow a safe participation in the study.
- Enrolled in another study that could confound the results of this study, without documented pre-approval from a Medtronic study manager.

## **E STUDY PREPARATION PROCEDURES**

### **E.1 Investigator/Investigation site selection**

The role of the principal investigator is to implement and manage the day-to-day conduct of the clinical study as well as ensure data integrity and the rights, safety and well-being of the subjects involved in the clinical study.

The NUTRIM School of Nutrition and Translational Research in Metabolism of the Faculty Health, Medicine and Life Sciences, Maastricht University and the Investigator, [name], have been included in the study since they both comply with the following requirements:

- investigator's qualification: Investigator is qualified by training, education, and relevant experience appropriate to the use of the products and associated procedures; Investigator expects to have adequate time and resources to conduct the study throughout the duration of the study; Investigator has access to an adequate number of eligible subjects; Ability to comply with applicable EC and regulatory requirements; Investigator is not debarred, disqualified, or working under sanctions in applicable region
- sufficient patient population/referral base
- sufficient resources to conduct the study
- facilities and administrative support
- experience in the field of walking patterns
- past experience in conducting research in this area

Furthermore, the site is one of the few centers in Europe with the CAREN (computer Assisted Rehabilitation Environment) system.

#### *E.1.1 Clinical Investigation Agreement*

A Clinical Investigation Agreement shall be in place, signed by the participating investigation site and/or principal investigator of the investigation site, as per the local legal requirements, and returned to Medtronic prior to the commencement of any clinical study activities. The investigator is indicating approval of the Clinical Investigation Plan and subsequent amendments, by a fully executed agreement. Amendments to this Clinical Investigation Plan shall be agreed upon between Medtronic and investigator(s) and be recorded with a justification for the amendments.

#### *E. 1.2 Curriculum Vitae*

An up to date signed and dated curriculum vitae from each investigator and site staff participating in this clinical study, evidencing the required qualifications, including the year and where obtained, shall be collected and shall include their current position at the investigation site. The signature on the CV must be dated within 3 years prior to the date of activation of the site.

#### *E.1.3 Delegated task list*

A Delegated Task List (DTL), signed by the Principal Investigator, documenting the attribution of responsibilities for investigation site staff, including their initials, signature, title and responsibilities in the clinical study will be in place prior to study start.

### **E.2 Ethics**

#### *E.2.1 EC approval*

Prior to enrolling subjects in this clinical study, the investigation site's EC will be required to approve the current Clinical Investigation Plan, the Patient Information and Informed Consent

form, including any other written information to be provided to the subjects. EC approval of the clinical study must be received in the form of a letter and provided to Medtronic before commencement of the clinical study at an investigation site. The approval letter must contain enough information to identify the version or date of the documents approved. If this information is not contained in the approval letter, it must be retrievable from the corresponding submission letter. In addition, the approval letter needs to be accompanied by an EC roster or letter of compliance, to allow verification that the investigator, other investigation site personnel, and/or Medtronic personnel are not members of the EC. If they are members of the EC, written documentation is required stating that he/she did not participate in the approval process. If the EC imposes any additional requirements (e.g. safety reports, progress reports etc.), Medtronic will prepare the required documents and send them to the investigator for reporting to the EC. Investigator must inform immediately Medtronic of any change in status of EC approval once the investigation site has started enrolment. If any action is taken by an EC with respect to the study, that information will be forwarded to Medtronic by the investigator immediately. If any Amendment to this Clinical Investigation Plan will be developed it must be approved by EC prior its implementation.

### *E.2.2. Informed consent process*

The investigator or authorized designee must obtain written informed consent before any clinical study related activity takes place.

Well in advance of the consent discussion, the subject should receive the Medtronic and EC approved Patient Information and Informed Consent Form. During the consent discussion, the investigator or his/her authorized designee must fully inform the patient of all aspects of the clinical study that are relevant to the patient's decision to participate in the clinical study. If a patient is illiterate, an impartial witness must be present during the entire informed consent discussion. All items addressed in the Patient Information and the Informed Consent Form must be explained. The language used shall be native and as non-technical as possible and must be understandable to the patient and the impartial witness, where applicable.

The subject must have ample time and opportunity to read and understand the Patient Information and the Informed Consent Form, to inquire about details of the clinical study, and to decide whether or not to participate in the clinical study. All questions about the clinical study should be answered to the satisfaction of the subject.

Neither the investigator, nor the investigation site staff shall coerce, unduly influence or induce a patient to participate or to continue to participate in the clinical study. The informed consent process shall not waive or appear to waive the subject's rights.

When the subject decides to participate in the clinical study, the Informed Consent Form must be signed and personally dated by the subject and investigator or authorized designee. If applicable, the witness shall also sign and personally date the consent form to attest that the information in the Patient Information and Informed Consent Form was accurately explained and clearly understood by the subject, and that informed consent was freely given.

After all persons have signed and dated the Informed Consent Form, the investigator must provide the subject with a copy of the Patient Information and the signed and dated Informed Consent Form.

### *E.2.3 Revisions in Patient Information and Informed Consent Form*

Medtronic will inform the investigators whenever information becomes available that may be relevant to the subject's confirmed participation in the clinical study. The investigator or his/her authorized designee should inform the subject in a timely manner.

Medtronic will revise the written Patient Information and Informed Consent Form whenever new information becomes available that may be relevant to the subject's confirmed participation in the clinical study. The revised information will be sent to the investigator for approval by the EC. After approval by the EC, the Patient Information and Informed Consent Form must be provided to the to the participating subjects who have not completed the study, and the informed consent process as described above needs to be repeated.

#### *E.2.4 Regulatory notification / approval*

Since the Reveal LINQ will not be used for medical purposes during the study, but exclusively for technical reasons, the Reveal LINQ and REEF software are not considered a medical device as laid down in WMH Article 1, first paragraph. The medical devices used in the study are CE marked and used within their approved intended use; therefore no submission to Dutch Competent Authority is required.

### **E.3 Regulatory compliance**

This clinical study will be conducted in compliance with Declaration of Helsinki 2013, laws and regulations of the country in which the clinical study is conducted, including data protection laws, the Clinical Investigation Agreement and the Clinical Investigation Plan.

All principles of the Declaration of Helsinki have been implemented in this clinical study by means of the patient informed consent process, EC approval, clinical study training, clinical trial registration, preclinical testing, risk benefit assessment, publication policy, etc.

### **E.4 Training requirements**

Prior to investigation site activation or subsequent involvement in clinical study activities, Medtronic will provide clinical study training relevant and pertinent to the involvement of personnel conducting clinical study activities and investigator responsibilities.

As a minimum the CIP, PIC, use of data collection tools, applicable local regulations, as well as device training are required. Study-specific training will be documented prior to investigation site activation.

### **E.5 Study materials and study-specific equipment**

The sponsor will supply all required study materials for appropriate data collection before study start as the Paper CRFs and the Investigator Site File to maintain required study documentation.

The Sponsor will also provide the following clinical study-specific equipment, after the Clinical Study Manager has declared the investigation site ready to start the clinical study:

- 3-D accelerometer – ActiGraph wGT3X-BT
- Accelerometer - Reveal LINQ (including the 2090 programmer to upload/download the REEF software)
- DR220 Holter

These devices are the property of Medtronic, and will be collected by Medtronic personnel at the completion of the study.

It is the investigator's responsibility to ensure the CAREN (computer Assisted Rehabilitation Environment) system will be available at the Site for the Study procedures.

All reusable devices need to be cleaned/sanitized after each deployment as per clinical practice.

### **E.6 Study device and equipment traceability**

#### *E.6.1 Supply of devices and equipment*

The Reveal LINQ (Study device) and the monitoring equipment will be provided free of charge by the sponsor for the duration of the study. The Reveal LINQ should be used only in this clinical study according to the CIP. Medtronic will only allow shipment of study device and equipment to the investigation site or investigator, after the Clinical Study Manager has declared the investigation site ready to start the clinical study. Medtronic will register the shipment and receipt of the devices at the sites.

### *E.6.2 Storage & handling of study devices and equipment*

The study device and the equipment must be stored in a secured area. The method of storage shall prevent the use of study device for other applications than mentioned in this Clinical Investigation Plan.

### *E.6.3 Device and equipment return procedures*

At the end of the study, the device and the equipment provided by Medtronic will be returned to Medtronic. The Sponsor will ensure collection of all the device and equipment at the end of the study.

### *E.6.4 Device and equipment disposition requirements*

Each study device and monitoring equipment component provided to the site will be traced during the clinical study recording on a specific device tracking log, with the relative serial numbers, with date of receipt and final return date to Medtronic. The investigator is responsible for maintenance of each Device Tracking Log in the Investigator Site File. On this log, the receipt, return and disposal of the study devices shall be documented. At the end of the clinical study the principal investigator must sign and date the original Device Tracking Logs. In addition, all information on the use, storage and handling of the product and download of the investigational software will be provided under a separate cover

## **F STUDY METHODS**

### **F.1 Point of enrollment**

The point of enrollment is the time when a subject signs and personally dates the Informed Consent Form. At that point, the subject is considered enrolled in the investigation.

The investigator will maintain a log of all subjects enrolled in the study, assigning an identification code linked to their names, alternative subject identification or contact information.

### **F.2 Baseline**

The Baseline visit can be a standalone visit or can be performed on the same day of the walking exercises prior to perform the tests. In the case the walking exercise visit is a standalone visit, it needs to be done within 1 month of the baseline.

The following baseline information will be collected:

- Patient informed consent,
- Inclusion/exclusion assessment,
- Relevant Medical History,
- Subject Demographics
- Physical Examination, (i.e. height, weight, blood pressure, heart rate)
- Ongoing Relevant Medications.

### **F.3 Walking exercises**

No devices are implanted in this study. Before the Walking protocol is initiated the RAMware will be downloaded onto the device via the 2090 programmer.

At the beginning of the walking exercises:

- The Reveal LINQ memory will be cleared
- The Reveal LINQ, the accelerometers and the DR220 Holter monitor will be placed on the subject. A medical-grade adhesive will be placed underneath the Reveal LINQ as an additional safety measure aiming to avoid direct contact with the patient's skin
- Time will be recorded;

- The Reveal LINQ and the Actigraph will be manually tapped simultaneously to provide a marker for the further data analysis;

The following exercises will be performed:

- Six Minute Walk (6MW) Test

The 6MW test measures the distance an individual is able to walk over a total of six minutes on a flat surface. The goal is for the individual to walk as far as possible in six minutes. The 6MW test will be performed within the CAREN system environment

- 4 Meter Gait Speed (4MGS) Test

The 4MGS test measures the gait speed an individual is able to walk over 4 meters on a flat surface. The goal is for the individual to walk as fast as possible over 4 meters.

It will be repeated 3 times within the aforementioned 6MW test (after approximately 1, 3 and 5 minutes) to get variability due to subject tiredness. The test will be performed within the CAREN system environment.

- Five Times Sit to Stand (FTSTS) Test

The STS test measures the time a subject takes to stand up from an armchair 5 times in a row, without stopping in between. It is a short test which measures dynamic balance and functional mobility.

- Expanded Timed Get-Up-and-Go (ETGUG) Test

The ETGUG test measures the time it takes a subject to stand up from an armchair, walk a distance of 10 m, turn, walk back to the chair, and sit down. It is a short test of basic mobility skills for frail community-dwelling elderly.

To minimize potential bias due to subject tiredness and fatigue during the execution of the physical tests:

- The order of the tests will be randomly defined at discretion of the investigator;
- A resting time between tests may be granted, at discretion of the investigator.

The tests may or may not be conducted by the same investigator.

Upon completion of the walking exercises the Reveal LINQ device as well as the Holter and the Accelerometers will be removed from the subject and the subject's participation in the study will be complete. A Study Exit form will be completed.

Upon completion of the study the RAMware will be removed from the LINQ device.

## F.4 Data collection requirements

The following data will be collected as summarized in the table below:

- Demographic data for patients, Relevant medical history, Medications, Subject demographics, Physical Examination, Inclusion/exclusion assessment.
- Device Data: LINQ/Holter, Actigraph and CAREN system data, during the Tests

Table 1 – Data collection requirements		
Study Procedure	Enrollment/Baseline	Walking Exercises Visit
Patient informed consent	x	
Inclusion/exclusion assessment	x	
Relevant Medical History	x	
Demographics	x	
Physical examination	x	
Medications	x	
REEF software upload/download		x
LINQ placement		x
Holter placement and recording		x
Accelerometer placement and recording		x
ETGUG test		x
FTSTS test		x
6MW test		x
4MGS test		x
Exit subject	As they occur	
Study deviations	As they occur	

## F.5 Role of the sponsor's representatives

Sponsor representatives may provide support as required for the study under supervision of the Principal Investigator, including:

- Provide study training relevant and pertinent to the involvement of personnel conducting study activities and investigator responsibilities
- Technical support at all visits under the supervision of a study investigator, but no data entry, shall be performed by Medtronic personnel or their representatives at sites.
- Provide clarification in case of need on correct completion and/or correction of CRFs
- Monitoring and auditing activities

The sponsor's representatives providing technical support may be listed on the sponsor's technical support list

## F.6 Source documents

Regular hospital charts are considered source documentation. Also files collected on SD cards from the LINQ/ the Holter, the 3-D Accelerometer and on an external Hard Drive from the CAREN System are considered source data. The study paper CRFs, signed and dated by the investigator or an authorized designee can be used as source document for the data collection points specified in table 4; See table below for each data specific source document. See table below for each data specific source document.

Table 2 – Source Documents	
Data	Source Document
Inclusion/exclusion assessment	Patient Hospital chart/worksheets
Relevant Medical History	Patient Hospital chart/worksheets
Demographics	Patient Hospital chart/worksheets
Physical examination	Patient Hospital Chart/worksheets
Medications	Patient Hospital Chart/worksheets
LINQ data/Holter data	SD Card
3-D Accelerometer Data	SD Card
CAREN System data	External Hard Drive

The investigator will clearly mark clinical records to indicate that the subject is enrolled in this clinical study.

The access to source documents must be guaranteed as reported in section G 2.2.

### F.7 Adverse events and Device Deficiency

No MDT CE market release device involved in the study considered as medical device; it will be responsibility of the investigator to report all product complaint(s) associated with a medical device distributed by Medtronic of any other manufacturer.

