### *G.1.2 Source data to be directly recorded on the Case Report Forms*

The following data will be recorded directly on the CRF and is considered as source data:

ETGUG data, FTSTS timing, Gait speed (4MGS test), Distance covered in 6 minutes (6MW test). Refer to Table 3 for further details:

Table 3 –Source data to be directly recorded on CRFs	
Data	Source Document
LINQ placement	CRF
Holter placement and recording	CRF
Accelerometer placement and recording	CRF
ETGUG test	CRF
FTSTS test	CRF
6MW test	CRF
4MGS test	CRF
Exit subject	CRF
Study deviations	CRF

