### *G.3.2 Early investigation site suspension or termination*

Medtronic or EC may decide to suspend or prematurely terminate an investigation site (e.g. in case of expiring approval of the reviewing EC, non-compliance to the Clinical Investigation Plan or lack of enrollment). If an investigation site is suspended or prematurely terminated, Medtronic shall promptly inform the investigator of the termination or suspension and the reason(s) for this. The investigator shall then promptly inform the reviewing EC, the study subject and their General Practitioner. When the risks are found to outweigh the potential benefits or when there is conclusive proof of definite outcomes, investigators must assess whether to continue, modify or immediately stop the clinical study in the respective investigation site and immediately inform the sponsor and EC if applicable.

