**1.3 Records and reports**

*1.3.1 Investigator records*

At a minimum, the following records must be kept by the investigator:

- Clinical Investigation Plan and, any amendments
- EC notification, correspondence and approval
- EC voting list
- Medtronic and EC approved Patient Informed Consent
- Fully signed clinical investigation agreement and confidentiality agreement (if not included in the clinical investigation agreement)
- Insurance certificates
- Completed Delegated Task List and Curriculum Vitae of all investigation site personnel
- Training documentation of all investigation site personnel
- Relevant communications that pertains to the clinical study
- Subject identification log
- Signed, dated and fully executed informed consent forms
- Fully executed CRFs and corrections
- Device accountability records
- Final report

All study related information and records are subject to inspection and must be retained for a period of two years after study termination or closure or longer if required by local or hospital regulations

*1.3.2 Investigator reporting responsibilities*

The investigator is responsible for the preparation (review and signature) and submission to Medtronic of all case report forms and deviations from the clinical investigation plan. If any action is taken by the EC with respect to the study, the information must be forwarded to Medtronic immediately. Reports are subject to inspection and to the retention requirements as described above for investigator records. The investigator shall prepare and submit in a complete, accurate and timely manner the reports listed in Table 4.

Table 4: Investigator Reports		
Reports	Submit To	Description / Constraints
Withdrawal of EC approval	Medtronic	Notification immediately after the investigator first learns of withdrawal of EC approval.

Table 4: Investigator Reports		
Reports	Submit To	Description / Constraints
Study Deviations	Medtronic, EC, as applicable	Any deviation from the CIP shall be recorded together with an explanation for the deviation. Deviations shall be reported to the sponsor who is responsible for analyzing them and assessing their significance.  Note: When relevant, Ethics Boards, competent authorities or the appropriate regulatory bodies should be informed.
Failure to obtain informed consent	Medtronic, EC	Notification within five working days.
Progress Reports and final report (if required)	Medtronic, EC	Provide if required by local law or Ethics Board

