### *1.3.4 Sponsor reporting responsibilities*

Medtronic shall prepare and submit the complete, accurate, and timely reports listed in Table 5. In addition, Medtronic shall, upon request of reviewing EC or regulatory agency, provide accurate, complete and current information about any aspect of the study.

Table 5: Sponsor Reports		
Report	Submit to	Description
Early termination or suspension of the clinical study	Investigator	Provide prompt notification of termination or suspension and reason(s)
	EC	Inform the EC promptly, if required per local law
Withdrawal of EC approval	Investigator	Notify all applicable investigators, if required by local laws or EC
Progress Reports	EC	Submit to EC, if required per local law
Final Report	EC	Submit to EC, if required per local law
Study Deviation	Investigator	Site specific study deviations will be submitted to the investigator quarterly.

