### J.2 Risks

Since the study devices will not be used for therapeutic purposes, but just to collect accelerometer data and considering the nature and duration of the study, no major risks to the subjects are expected with this study. It may be possible to anticipate local events at the level of the study tool/product placement (i.e. Allergic reaction, Skin irritation) - which the medical grade adhesive placed below the device should prevent - and/or events related to the physical execution (i.e. accidental fall) of the walking exercises.

Any further detail coming from risk assessment on potential risks and risks minimization will be provided under a separate cover.

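### The CIP anticipates falls and skin reactions and promises a safety report, but defines no systematic recording or reporting of adverse events

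*Protocol*

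**What the plan says.** **Events foreseen.** CIP J.2 expects no major risk but names two kinds of event. At the placement sites: "It may be possible to anticipate local events at the level of the study tool/product placement (i.e. Allergic reaction, Skin irritation". During the tests: "events related to the physical execution (i.e. accidental fall) of the walking exercises".

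**Duty to report.** CIP F.7 is headed as the section on adverse events and device deficiency. Its only instruction is that "it will be responsibility of the investigator to report all product complaint(s) associated with a medical device". It also states that none of the sponsor's devices in the study counts as a medical device. E.2.4 and B.2 say the same of the Reveal LINQ.

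**Data and reports.** In Table 1 (F.4) the only event-driven rows are subject exit and deviations ("Study deviations As they occur"). Table 3 (G.1.2), introduced by "The following data will be recorded directly on the CRF and is considered as source data", covers placement and recording, the four tests, exit and deviations. Section I.3.2 makes the investigator responsible for "submission to Medtronic of all case report forms and deviations from the clinical investigation plan", and Table 4 has no adverse-event report. Section I.3.4 says "Medtronic shall prepare and submit the complete, accurate, and timely reports listed in Table 5", and that table has none either.

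**Analysis.** CIP H.1 undertakes to report safety for everyone who consented. SAP 7.10 plans no safety analysis because the LINQ is treated as a non-medical device. SAP 7.12 states that nothing major departs from the protocol's analyses.

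**The concern.** The plan foresees specific harms and commits to a safety report, but no data item feeds that report. F.7 covers complaints about products. A fall during a walking or sit-to-stand test is not one.

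Two things are at stake. The first is what the report can conclude. If nobody is asked to write events down, a statement that no safety problem was seen would describe the collection method rather than the subjects. The second is oversight. G.3.2 has the investigator act "When the risks are found to outweigh the potential benefits", and G.3 lets the sponsor, a regulatory authority or the EC suspend the study or the site. The CIP defines no event record on which any of them would base that judgment. Subjects have NYHA class II or III heart failure, are asked to walk as far and as fast as they can (F.3), and have no direct benefit (J.1). I.2 provides for no safety committee.

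**Working it through.** The point rests on comparing passages. The plan gives no safety figure to reproduce.

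**Step 1. Is there a data item or report for an adverse event?**

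| Place in CIP | Content | Adverse-event item |
|---|---|---|
| F.7 | Product complaints about a medical device | None |
| Table 1 (F.4) | Baseline items, placement, tests, exit, deviations | None |
| Table 2 (F.6) | Source documents for baseline and device data | None |
| Table 3 (G.1.2) | Placement, tests, exit, deviations on CRF | None |
| Table 4 (I.3.2) | EC withdrawal, deviations, consent failure, progress and final reports | None |
| Table 5 (I.3.4) | Termination, EC withdrawal, progress and final reports, deviations | None |

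In the CIP's own terminology, AE and ADE occur only as entries in the abbreviation list (L.3).

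**Step 2. Could another route carry the event?**

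- *Deviation form.* F.9 defines a deviation as the site not following the CIP or the agreement. A fall during a correctly run test is not one. The deviation reasons in SAP 7.1.2 (consent, eligibility, data collection) include no event category.
- *Emergency deviation (F.9.1).* Reaches the sponsor and, if applicable, the EC, but only if the investigator departs from the CIP.
- *Study Exit CRF (F.8).* On withdrawal, gives the reason and any relationship to the study, and CRFs go to the sponsor. F.8 describes nothing comparable for a subject who completes.
- *G.3.2.* The investigator informs the sponsor and, if applicable, the EC, but only once risks are judged to outweigh benefits.
- *EC-imposed safety reports (E.2.1).* Only if the EC asks.
- *Monitoring (G.2).* Gives access to hospital records, but the CIP does not require a fall or rash at the visit to be entered there.
- *Product complaint (F.7).* A skin reaction under the Holter or ActiGraph might be handled this way. Under the LINQ, F.7's wording excludes it, because the LINQ is declared not to be a medical device.

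Each route is conditional. None requires a record of a fall, or of a skin reaction under the LINQ, after which the subject continues.

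**Step 3. Do the two documents agree on safety?** H.1 promises a report on all consented subjects, SAP 7.10 drops it, and SAP 7.12 does not list that as a change.

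**Step 4. Scale, for illustration.** With n = 20 (C.7) and an assumed per-subject risk p, the chance of at least one event is 1 − (1 − p)^20:

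- p = 1%: 1 − 0.99^20 = 0.182
- p = 2%: 1 − 0.98^20 = 0.332
- p = 5%: 1 − 0.95^20 = 0.642
- p = 10%: 1 − 0.90^20 = 0.878

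If every event were recorded and none occurred, the exact one-sided 95% upper bound on p would be 1 − 0.05^(1/20) = 0.139, or 13.9%.

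**The case against.** The best defence is that light safety procedures were chosen deliberately. The devices are external, nothing therapeutic is tested, I.2 and J.2 give reasons for expecting no major risk, and subjects are protected by the exclusion criteria, discretionary rest between tests and the investigator's power to withdraw them. The investigator sees each event first hand. E.3 also binds the site to national law, whose reporting duties cannot be seen here.

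Much of this stands. A reader might infer that nobody able to stop the study would ever learn of an event, or that the number reported must be zero. The documents do not support that, because the conditional routes in Step 2 exist and G.3.2 tells the investigator to inform the sponsor and, if applicable, the EC. A reader might also infer that no study form has space for an adverse event. That cannot be checked: the CRFs (L.2) and further risk-assessment detail (J.2) are under separate cover. Only absence from the CIP's tables can be shown.

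The defence does not reach the core. How the LINQ is classified has no bearing on whether a subject falls. A deliberate decision not to collect safety data would also contradict H.1. The 13.9% bound shows that 20 subjects can say little about rare harm even with full recording. That limits what the data could prove, but it does not remove the need to record events the plan itself foresees.

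**Conclusion.** The point holds in this form: the CIP anticipates falls and skin or allergic reactions and promises a safety report, but defines no systematic way to record or report adverse events. An event after which the subject continues would reach the sponsor or EC only incidentally, and silence in the data would not be evidence of safety. The SAP widens the gap by planning no safety analysis without noting the departure from H.1.

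This rests on the text of F.7, Tables 1 to 5, H.1 and SAP 7.10 and 7.12, and on no assumed rate. The 18% to 88% range of Step 4 depends wholly on assumed risks of 1% to 10%, pools falls with minor skin irritation, and measures how often an event would occur, not how often one would go unreported. If the unseen CRFs do include an adverse-event page, the CIP's tables still need correcting, but less would be lost. The change should be made; the primary comparison of gait parameters does not depend on it.

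**What to change.** 1. Amend F.7 so that the investigator records on a CRF every fall, every skin or allergic reaction and any other untoward event from consent to study exit, with the test or device concerned, severity and outcome.
2. Add an adverse-event row, completed as events occur, to Tables 1 and 3, and an adverse-event report row to Tables 4 and 5.
3. Reconcile F.7, J.2, H.1, G.3 and SAP 7.10. In the SAP, replace the statement that no safety analysis will be done with a descriptive listing of recorded events on the All Enrolled Population (called the Full Analysis Set in SAP 7.1.3), and correct SAP 7.12 to match.
4. If enrolment is already complete, state in the clinical study report that adverse events were not systematically collected, and list any that came to light by other routes.

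Cost: one CRF page, a few table rows, a short amendment and one listing. No added visit, procedure or staff for about 20 subjects.
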